5.0 Schedule of Assessments and Procedures

	Baseline (Pre-operative clinic visit)	Day 7-14	Post-Treatment safety assessment visit (Day 13 or 14)	Post-treatment sample	Follow-up visit POD 7-14
Tests & Observations					
History	X				X
Age/ECOG PS	X				
Physical Examination	X				X
Pulse, Blood Pressure	X		X		X
Weight/Height	X				
Drug Toxicity Evaluation		X	X		X
Study Drug Calendar		X	X		
EKG	X		X		
Pregnancy test within 2weeks of treatment (urine or serum)	X				
Laboratory Studies					
Ca, Mg, K, Cr, PT, PTT, Bilirubin, AST, ALT, Alk Phos, CBC	X				
Ca, Mg, K, platelets			X		
Treatment					
Placebo/Vandetanib 300 mg daily		X			
Staging Evaluations					
Pathologic Tumor Size				X	
Histology	X			X	
Tumor markers ¹	X			X	
Elston-Ellis Grade ²	X			X	
Lymph node status ³	X (CLINICAL)			X (PATHOLOGIC)	

Note: Staging determinants can be obtained on the baseline or post-treatment sample. They do not need to be obtained on both, but should reflect the final conclusions of the pathologist.

¹ Tumor markers are Estrogen Receptor, Progesterone Receptor and Her2/neu. See Section 9.2.

² Eliston-Ellis Grade is a pathological term for tumor aggression.

³ Lymph node status will be recorded in accordance with preoperative (clinical) and postoperative (pathologic) staging.

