6.0 Treatment Plan

Subjects meeting the eligibility requirements in Section 4.1 and who have given signed informed consent will start the treatment dose of Vandetanib 300 mg or placebo orally, daily, starting such time as to allow 7 to 14 doses with the 7th or 14th dose given on the morning of the operation. Patients will return to clinic the day before the scheduled operation or the morning of surgery for repeat laboratory studies and EKG. Costs of the post-treatment labs and EKG will be covered by the PI. The results will be reviewed and safety to proceed documented prior to the operation. The study calendar (which will be provided at the pretreatment office visit to document administration of the study drug and any side effects associated with treatment) will be reviewed, pill counts performed, and an adverse events assessment performed at that time. Any concerns related to toxicities and safety to proceed to surgery will be addressed with the attending surgeon at that time. Common induction anesthetics (isoflurane, desflurane and sevoflurane) can cause QTc prolongation. Any QTc (>440 ms) on EKG should be discussed with the attending anesthesiologist prior to induction, and these induction agents should not be used if QTc > 480 ms. A flow chart of the preoperative screening procedure is shown in appendix 3. Subjects will be instructed to take their medication at the same time each day. In general subjects should take their dose every day even if it is not at the recommended time. Specific questions regarding timing and doses can be directed to [name] [contact], [name]). Patients will be removed from the study for failure to take at least 80% of the study doses. Patients will not be replaced if they are removed from the trial.

Women of Childbearing Potential (WOCBP) must use *highly effective* methods of birth control (one method or a combination of methods that results in a less than 1% failure rate per year) throughout therapy and must maintain full contraception for at least 95 days after the last dose of Vandetanib.

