9.3 Follow-up Post Surgery

After surgery, the subject will return to clinic for a post-operative visit. This will involve a final drug toxicity evaluation. This is also the standard of care post-operative follow-up visit.

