10.0 Removal of Subjects from Protocol Therapy

10.1 Duration of Treatment

Subjects will continue vandetanib or placebo up to and including the morning of surgery for a total of 7 to 14 days. The time frame from preoperative clinic visit until definitive surgery will be a minimum of 2 weeks and the maximum of 4 weeks. Subjects with an adverse reaction of CTCAE grade III or higher will discontinue the study drug. Subjects can voluntarily discontinue the drug at any time during the trial, be removed from the drug at the discretion of their treating physician, or be discontinued by the study investigators. In previous trials with vandetanib, surveillance labs and toxicity assessment has been performed at two weeks of treatment, which will be done in this trial with the preoperative safety assessment. Because subjects will have already discontinued the study drug at that time it will not be possible to discontinue the study drug early based on that assessment. Due to the short duration of treatment in this trial and the low incidence of adverse reactions over that time frame in previous phase I and II trials we do not expect a significant number of severe adverse reactions. Subjects will be evaluated for study withdrawal if noncompliant with requirement for therapy, or if they are experiencing drug related toxicity. If the date of surgery is unexpectedly changed after initiation of treatment, the patient will continue treatment, including the morning of surgery, for not more than 28 total days.

10.2 Extraordinary Medical Circumstances:

If at any time the constraints of this protocol are detrimental to the subject's health and/or the subject no longer wishes to continue protocol therapy, remove the subject from the protocol treatment. In this event:

- Document the reason(s) for ending treatment on the follow-up form.
- The primary outcomes of response of down regulation of Ki-67 and secondary outcomes of evaluation of tumor markers in the baseline and endpoint tissue samples will be analyzed unless the subject withdraws consent to do so.

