11.2.2 Assessment of Risk Level

The Data Safety Monitoring Plan (DSMP) can be found in Appendix 5 of this protocol.

This investigation involves a risk-level 3 procedure, in a population that should not be at any increased risk for complications.

11.2.3 Assessing Toxicity:

Toxicity will be graded according to NCI’s Common Toxicity Criteria (CTCAE v4). The investigator will determine relationship of toxicity to the investigational drug as unrelated, unlikely related, possibly related, probably related, or definitely related using standard criteria for clinical trials. All grades of toxicity will be noted and reported as directed in Table I: Clinical Data Update System (CDUS) Guidelines for Routine Adverse Event Reporting.

Patients who experience a CTCAE (version 4) Grade 3 or 4 toxicity that is considered related to Vandetanib will have their study drug stopped. If a patient discontinues treatment, safety follow-up visits will be performed according to the schedule of assessments and procedures. In addition, a 30 day follow up visit will occur if AEs have not resolved by the time of the post op safety visit. SAEs and study drug-related AEs must be followed until resolution unless in the Investigator’s opinion, the event is unlikely to resolve due to the patient’s underlying condition.

Cardiac toxicity - QTc prolongation

Electrocardiograms will be evaluated by suitably qualified personnel for the presence of QTc prolongation or other abnormalities, in particular, any changes in the T-wave morphology that would suggest a higher likelihood for the development of any arrhythmia. Any clinically significant abnormal findings or QTc prolongations will be recorded as AEs.

In addition to scheduled ECG, additional ECGs should also be performed in the event of QTc prolongation, both during and post the prolongation period.

- During the QTc prolongation period: For a single QTc value of >500 ms, Vandetanib must be withheld and patients will be removed from the study. Electrocardiograms will be followed at least once per week (done at the same day each week) along with electrolytes, until QTc falls \leq 480 ms.

Gastrointestinal toxicity

Nausea, vomiting, or both may be controlled with anti-emetic therapy. The use of somatostatin or a somatostatin analogue is allowed to control diarrhea.

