Diarrhea should be treated with standard medications to avoid dose modification or interruption, if possible. Electrolyte supplementation with regular laboratory monitoring should be used, when appropriate, to maintain electrolytes within normal limits and prevent an increased risk of QTc prolongation.

If CTCAE Grade 3 or 4 diarrhea develops, patients will be removed from the study. Any electrolyte imbalance must be promptly corrected since hypokalemia and hypomagnesaemia are potential risk factors for drug-induced arrhythmia.

Cutaneous toxicity

It is strongly recommended that all patients follow a program of sun protective measures (wearing additional clothing and/or sunscreen) while receiving study treatment and for 3 to 4 weeks after discontinuing study treatment. The aim is to reduce the risk of development of skin rash, or minimize the severity of skin rash, and to minimize the requirement for dose reduction of study therapy.

If a patient develops a skin rash, the following actions are recommended to the Investigator for the management of this reaction:

- A variety of agents can be used to manage skin rashes. These include mild to moderate strength steroid creams or systemic glucocorticoids, either topical or systemic antibiotics, topical or systemic antihistamines, and occasionally retinoid creams.
- The rash should be graded as soon as possible according to the CTCAE cutaneous toxicity criteria.
- If a rash of CTCAE Grade 2 or higher is detected, immediate symptomatic treatment should be provided.
- If a rash of CTCAE Grade 3 or 4 is detected, patients will be removed from the study

Hypertension

Patients who develop CTCAE Grade 3 hypertension may continue on therapy if blood pressure is controlled on increased anti-hypertensive medication (to CTCAE Grade 1 or baseline). If blood pressure cannot be stabilized with increased anti-hypertensive medication, patients will be removed from the study.

Patients with CTCAE Grade 4 hypertension must be removed from the study.

11.2.4 Adverse Event Reporting:

Table I:

Clinical Data Update System (CDUS) Guidelines for Routine Adverse Event Reporting

Attribution	Adverse Event				
	Grade 1	Grade 2	Grade 3	Grade 4	Grade 5
Unrelated	Not required	Not required	CRSO	CRSO	CRSO
Unlikely	Not required	Not required	CRSO	CRSO	CRSO
Possible	CRSO	CRSO	CRSO	CRSO	CRSO
Probable	CRSO	CRSO	CRSO	CRSO	CRSO
Definite	CRSO	CRSO	CRSO	CRSO	CRSO

Reports are collected by the CRSO or DSMB and communicated to the DSMC

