Amiodarone Anastrozole Aprenavir Azithromycin Bromocriptine Cannabinoids Cimetidine Cisapride Clarithromycin Clotrimazole Cyclosporine Danazol Delavirdine Dexamethasone Diethyldithiocarbamate Diltiazem Dirithromycin Disulfiram Entacapone (high dose) Erythromycin Ethinyl estradiol Fluconazole Fluoxetine Fluvoxamine Gestodene Grapefruit juice Indinavir Isoniazid Itraconazole	Ketoconazole Metronidazole Mibepradil Miconazole Nefazodone Nelfinavir Nevirapine Norfloxacin Norfluoxetine Omeprazole Oxiconazole Paroxetine Propoxyphene Quinidine Quinine Quinupristin and dalfopristin Ranitidine Ritonavir Saquinavir Sertindole Sertraline Telithromycin Troglitazone Troleandomycin Valproic acid Verapamil Zafirlukast Zileuton

Appendix 2
List of Drugs with Potential Interactions
Examples of medications known to prolong the QT interval and/or induce Torsades De Pointes (TDP)

It has been recognized for a number of years that certain prescription medications can prolong the QT/QTc interval and cause a form of acquired Long QT syndrome, known as drug induced LQTS. The drugs that prolong the QT interval and/or have a risk of inducing Torsades de Pointes (TdP) are listed below. We have divided these into two groups based on their known or perceived risk of causing TdP:

A. Group 1: Drugs that are generally accepted by authorities to have a risk of causing Torsades de Pointes

Concomitant use of these drugs is not allowed during the study or within 2 weeks of randomization (at least four weeks for levomethadyl). These drugs should also be avoided for **up to 4 weeks following discontinuation of study treatment:**

Table 1 Group 1 Drugs^a

Generic Name	Class/Clinical Use	Comments
Amiodarone	Anti-arrhythmic/abnormal heart rhythm	Females>Males, TdP risk regarded as low
Arsenic trioxide	Anti-cancer/Leukemia	
Astemizole	Antihistamine/Allergic rhinitis	No Longer available in U.S.
Azithromycin	Antibiotic/bacterial infection	
Bepridil	Anti-anginal/heart pain	Females>Males
Chloroquine	Anti-malarial/malaria infection	
Chlorpromazine	Anti-psychotic/Anti-emetic/schizophrenia/nausea	
Cisapride	GI stimulant/heartburn	No longer available in U.S.
Citalopram	Anti-depressant/depression	
Clarithromycin	Antibiotic/bacterial infection	
Disopyramide	Anti-arrhythmic/abnormal heart rhythm	Females>Males
Dofetilide	Anti-arrhythmic/abnormal heart rhythm	Females > Males
Domperidone	Anti-nausea/nausea	Not available in U.S.
Droperidol	Sedative;Anti-nausea/anesthesia adjunct, nausea	

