Investigator-initiated (Iowa)

Investigator-initiated, multi-center (non-Iowa)

- Is this study monitored by an outside DSMB? Yes No

Compassionate-use drug protocol

Pilot study

Phase I

Phase I/II

Phase II

Phase III

Phase IV

Study risk-level (refer to attached risk-level assessment for this study):

Level 1—low risk of morbidity or death, * <<1% of death or any adverse event

Level 2—risk of death* <1% or any adverse event 1% – 5%

Level 3—risk of death* 1% – 5% or grade 4 – 5 SAE 1% – 5%

Level 4—risk of death* >5% or grade 4 – 5 SAE >15%

Drugs being used on a “compassionate” basis

** Risk of death” refers specifically to 100-day treatment-related mortality*

The following additional documents will be included in the DSMP for this study:

- A subject eligibility check-list (inclusion / exclusion criteria), which will be available in OnCore, the HCCC CTMS
- A list of expected toxicities and stopping rules for suspension of accrual secondary to adverse events and safety parameters
- A signed and dated statement from the Principal Investigator(s) declaring any conflict of interest (or lack thereof) with a description of how a conflict of interest will be monitored to enhance transparency
- The Human Subjects application will be obtained from HawkIRB
- Future Continuing Review and/or Modification forms will be obtained from HawkIRB
- For multi-centered trials, a detailed description of the procedures in place at each center that enable communication between participating centers such that the PI is aware of the status of participating subjects including the immediate (<24hours – week day) awareness of grade 4 – 5 SAE / death

Risk Level 3

- An independent Study Monitor, or the DSMC Chair (or his designee), will review study data (provided by the PI and CRSO) and communicate with the PI at least twice yearly. The proceedings of this meeting will be summarized by the CRSO in a brief letter to the PI, a copy of which will be forwarded to the DSMC.
- Principal Investigator will provide a QUARTERLY report to the Study Monitor and the CRSO for the DSMC, or data may be obtained from OnCore:
 - Quarterly patient accrual data
- Copies of all Serious Adverse Events will be reported to the CRSO as per DSMC reporting guidelines.
- CRSO will conduct a BIANNUAL audit of at least 25% of the subjects' research charts, and will report the results to the DSMC. Audits will:
 - Validate eligibility of patients accrued to the study

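### New adverse events have no scheduled ascertainment after the post-operative visit (7 to 14 days after the last dose for completers), although the protocol's own precautions after treatment run 3 to 4 weeks

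*Combined protocol and SAP*

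**What the plan says.** The last column of the schedule in Section 5.0 is "Follow-up visit POD 7-14", and the drug toxicity row is marked there. Section 9.3 describes the same visit: "This will involve a final drug toxicity evaluation". Section 10.1 fixes the last dose relative to surgery: "Subjects will continue vandetanib or placebo up to and including the morning of surgery for a total of 7 to 14 days".

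Section 11.2.3 provides one later contact, under a condition: "In addition, a 30 day follow up visit will occur if AEs have not resolved by the time of the post op safety visit". The day from which the 30 days are counted is not given. The same section requires serious and drug-related events that are already known to be followed to resolution, with an exception for events unlikely to resolve.

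Three precautions reach past the post-operative visit:

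- Section 11.2.3, Cutaneous toxicity: sun protection "while receiving study treatment and for 3 to 4 weeks after discontinuing study treatment".
- Appendix 2, Group 1 QT-prolonging drugs: to be avoided for "up to 4 weeks following discontinuation of study treatment".
- Section 6.0: women of childbearing potential "must maintain full contraception for at least 95 days after the last dose of Vandetanib".

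Section 11.2.4 requires all serious adverse events and all pregnancy outcomes to be reported to the drug supplier. It puts no end date on either duty.

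**The concern.** The 30-day visit is triggered by what is already known at the post-operative visit. A patient with an open event is seen again. A patient with none is not asked again, so a rash, arrhythmia symptom or other event that starts later has no scheduled point at which it would be found. Yet the protocol asks patients to keep taking precautions against skin reactions and QT prolongation during just that time.

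Concomitant drugs have the same gap. Section 8.0 reviews them at entry and at scheduled assessments and requires no continuous record, so a Group 1 drug started after the post-operative visit but inside the 4-week period would not be recorded by plan.

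What is at stake is the completeness of the safety record. Appendix 5 has cumulative adverse-event reports assessed for trends, and that review sees only what is collected. The primary Ki-67 endpoint uses the biopsy and the surgical specimen and is unaffected.

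**Working it through.** The plan states no figure for the length of safety follow-up after the last dose, so there is none to reproduce. The check is date arithmetic.

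**Inputs**

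- Last dose, for patients who dose as planned: morning of surgery (Sections 6.0 and 10.1), taken as day 0.
- Last scheduled safety contact: post-operative day 7 to 14 (Sections 5.0 and 9.3), hence 7 to 14 days after the last dose.
- Precaution periods: 3 to 4 weeks, or 21 to 28 days (sun protection); up to 4 weeks, or 28 days (Group 1 drugs); at least 95 days (contraception).

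**Formula**

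Days without scheduled contact = precaution period − day of the post-operative visit.

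| Period | Visit on day 7 | Visit on day 14 | Share covered by the visit |
|---|---|---|---|
| 3 weeks | 21 − 7 = 14 | 21 − 14 = 7 | 7/21 to 14/21 = 33% to 67% |
| 4 weeks | 28 − 7 = 21 | 28 − 14 = 14 | 7/28 to 14/28 = 25% to 50% |
| 95 days | 95 − 7 = 88 | 95 − 14 = 81 | 7/95 to 14/95 = 7% to 15% |

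**Patients who stop early.** The 7-to-14-day figure does not apply to them. A patient who stops after the first of 14 planned doses has surgery 13 days later and is seen 13 + 7 = 20 to 13 + 14 = 27 days after the last dose. The gap concerns mainly patients who complete treatment.

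**The undefined 30-day count.** Placing the visit relative to the last dose needs an assumption about where the count starts:

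- From surgery (also the last dose in completers): day 30.
- From the post-operative visit: 30 + 7 = 37 to 30 + 14 = 44 days.
- From the first of 7 to 14 doses (6 to 13 days before surgery): 30 − 13 = 17 to 30 − 6 = 24 days.

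The possible range is thus 17 to 44 days after the last dose. Under the third reading the visit can fall before the end of a 4-week precaution.

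**Other scheduled safety data.** In Section 5.0 the last EKG and the last calcium, magnesium, potassium and platelet measurements belong to the pre-operative safety visit. The only pregnancy test is at baseline. Neither closes the gap.

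**What cannot be computed.** The documents list frequencies of side effects but no times of onset, so the number of events missed cannot be derived.

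**The case against.** The strongest reply is that the reporting duties have no end date. Section 11.2.4 requires every serious event to be reported whatever its cause, and every pregnancy outcome to be followed even after a patient has left the study. Grade 3 to 5 events go to the safety officer at any attribution. Known serious or drug-related events are followed to resolution, and a QTc above 500 ms is followed weekly until it falls to 480 ms or below. A reader might infer that late events and pregnancies go uncollected. The documents do not support that: such events are reportable once someone learns of them. Nor does any section say that trial participation ends at the post-operative visit. What remains is that a duty to report known events does not find unknown ones, and that mild or moderate new events are the least likely to reach the investigator unasked.

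It can also be said that a precaution period is not a stated duration of drug effect. This is correct. The periods show how long the protocol thinks caution is warranted; they do not prove that events occur throughout. One is a range starting at 3 weeks and another an upper limit, which is why both 3 and 4 weeks are shown above.

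Finally, a later contact will pick up surgical recovery and subsequent cancer treatment, with poor attribution in 40 patients per arm. That is a real cost. Collecting in the same way in both arms limits it, since such background events should on average be alike under randomisation.

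**Conclusion.** The point holds as a gap in active ascertainment. For patients who dose through the morning of surgery, a new event has no scheduled detection point for 7 to 14 days of a 3-week precaution period or 14 to 21 days of a 4-week one. Pregnancies in the last 81 to 88 days of the 95-day contraception period depend on passive reporting under a duty whose window is not defined. New non-serious events are the clearest loss. The result rests on the schedule being followed as written and on the last dose falling on the day of surgery.

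Two stronger readings are tempting and should not be drawn.

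- A reader might infer that the monitoring plan fails to observe the mortality that sets the trial's risk level, because Appendix 5 says risk of death "refers specifically to 100-day treatment-related mortality". That note defines categories on a monitoring form; it is not a follow-up commitment for this trial. Level 3 can also be met through the rate of grade 4 to 5 serious events, and the start of the 100 days is not given.
- A reader might infer that a planned comparison of adverse events between vandetanib and placebo is biased in the drug's favour. Section 2.0 lists only tissue-marker objectives and Section 12.0 plans no comparison of adverse events by arm, so there is no such planned analysis to bias.

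This is a worthwhile, inexpensive improvement to the safety record and not a threat to the primary result.

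**What to change.** In Sections 5.0, 9.3 and 11.2.3, replace the conditional 30-day visit with one phone or chart contact about 28 to 30 days after the last dose. It should cover every patient who took at least one dose, in both arms, and record new adverse events, new serious adverse events and any Appendix 2 Group 1 drug started since the last contact. Visits for unresolved events continue as now. Section 9.3 should then no longer call the post-operative toxicity evaluation the last one.

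State the day from which the 30 days are counted, and the end of the reporting windows for adverse events, serious adverse events and pregnancy. In doing so, reconcile Sections 5.0, 6.0, 9.3, 11.2.3 and 11.2.4 with Appendix 2; in particular, the pregnancy window should be reconciled with the 95-day contraception period. None of this changes a precaution, a dose or a rule for stopping treatment.

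The cost is protocol wording, one brief contact for each of up to 80 patients, a little coordinator time, and some unrelated post-operative events in the record. A further check of all patients at about day 100 is not needed to close this gap.

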Erythromycin	Antibiotic;GI stimulant/bacterial infection; increase GI motility	Females>Males
Flecainide	Anti-arrhythmic/abnormal heart rhythm	
Halofantrine	Anti-malarial/malaria infection	Females>Males
Haloperidol	Anti-psychotic/schizophrenia, agitation	TdP risk with I.V. or excess dosage
Ibutilide	Anti-arrhythmic/abnormal heart rhythm	Females>Males

Table 1**Group 1 Drugs^a**

Generic Name	Class/Clinical Use	Comments
Levomethadyl	Opiate agonist/pain control, narcotic dependence	Not available in U.S.
Mesoridazine	Anti-psychotic/schizophrenia	
Methadone	Opiate agonist/pain control, narcotic dependence	Females>Males
Moxifloxacin	Antibiotic/bacterial infection	
Pentamidine	Anti-infective/pneumocystis pneumonia	Females>Males
Pimozide	Anti-psychotic/Tourette's tics	Females>Males
Probucol	Antilipemic/Hypercholesterolemia	No longer available in U.S.
Procainamide	Anti-arrhythmic/abnormal heart rhythm	
Quinidine	Anti-arrhythmic/abnormal heart rhythm	Females>Males
Sotalol	Anti-arrhythmic/abnormal heart rhythm	Females>Males
Sparfloxacin	Antibiotic/bacterial infection	No longer available in U.S.
Terfenadine	Antihistamine/Allergic rhinitis	No longer available in U.S.
Thioridazine	Anti-psychotic/schizophrenia	
Vandetanib	Anti-cancer/Thyroid cancer	
(*Does not apply to this study)		

^a Source: www.QTdrugs.org. Last revised: 17 May 2012

B. Group 2: Drugs that in some reports may be associated with Torsades de Pointes but at this time lack substantial evidence of causing Torsades de Pointes.

Concomitant use of these drugs is not allowed within 2 weeks of randomization or during the study. These drugs will be allowed during the study, at the discretion of the Investigator, if considered absolutely necessary. In such cases, the patient must be closely monitored, including regular checks of QTc and electrolytes (reference Section 5.6.2 of the protocol).

Table 2**Group 2 Drugs^a**

Generic Name	Class/Clinical Use	Comments
Alfuzosin	Alpha1-blocker/Benign prostatic hyperplasia	
Amantadine	Dopaminergic/Anti-viral/Anti-infective/ Parkinson's Disease	
Artemether + piperaquine	Anti-malarial/	Not available in U.S.
Atazanavir	Protease inhibitor/HIV	
Chloral hydrate	Sedative/sedation/ insomnia	
Clozapine	Anti-psychotic/schizophrenia	
Dolasetron	Anti-nausea/nausea, vomiting	

Table 2**Group 2 Drugs^a**

[figure not shown]
Generic Name	Class/Clinical Use	Comments
Dronedarone	Anti-arrhythmic/Atrial Fibrillation	
Eribulin	Anti-cancer/metastatic breast neoplasias	

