Escitalopram	Anti-depressant/Major depression/Anxiety disorders	
Famotidine	H2-receptor antagonist/Peptic ulcer/ GERD	
Felbamate	Anti-convulsant/seizure	
Fingolimod	Immunosuppressant/Multiple Sclerosis	
Foscarnet	Anti-viral/HIV infection	
Fosphenytoin	Anti-convulsant/seizure	
Gatifloxacin	Antibiotic/bacterial infection	Oral/I.V. forms no longer available in U.S. and Canada, only ophthalmic
Gemifloxacin	Antibiotic/bacterial infection	
Granisetron	Anti-nausea/nausea and vomiting	
Iloperidone	Antipsychotic, atypical/Schizophrenia	
Indapamide	Diuretic/stimulate urine & salt loss	
Isradipine	Anti-hypertensive/high blood pressure	
Lapatinib	Anti-cancer/breast cancer, metastatic	
Levofloxacin	Antibiotic/bacterial infection	
Lithium	Anti-mania/bipolar disorder	
Moexipril/HCTZ	Anti-hypertensive/high blood pressure	
Nicardipine	Anti-hypertensive/high blood pressure	
Nilotinib	Anti-cancer/Leukemia	
Octreotide	Endocrine/acromegaly, carcinoid diarrhea	
Ofloxacin	Antibiotic/bacterial infection	
Ondansetron	Anti-emetic/nausea and vomiting	
Oxytocin	Oxytocic/Labor stimulation	
Paliperidone	Antipsychotic, atypical/Schizophrenia	
Perflutren lipid microspheres	Imaging contrast agent/Echocardiography	
Quetiapine	Anti-psychotic/schizophrenia	
Ranolazine	Anti-anginal/chronic angina	
Risperidone	Anti-psychotic/schizophrenia	
Roxithromycin*	Antibiotic/bacterial infection	*Not available in U.S.
Sertindole	Antipsychotic, atypical/Anxiety, Schizophrenia	Not available in U.S.

Table 2**Group 2 Drugs^a**

Generic Name	Class/Clinical Use	Comments
Sunitinib	Anti-cancer/RCC, GIST	
Tacrolimus	Immunosuppressant/Immune suppression	
Tamoxifen	Anti-cancer/breast cancer	
Telithromycin	Antibiotic/bacterial infection	
Tizanidine	Muscle relaxant/	
Vardenafil	phosphodiesterase inhibitor/vasodilator	
Venlafaxine	Anti-depressant/depression	
Voriconazole	Anti-fungal/anti-fungal	
Ziprasidone	Anti-psychotic/schizophrenia	

^a Source: www.QTdrugs.org. Last revised: 17 May 2012

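### Section 11.2.3 allows somatostatin analogues without condition, Section 8.0 and Appendix 2 restrict octreotide in two different ways, and the Appendix 2 checks have no interval

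*Combined protocol and SAP*

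**What the plan says.** Section 11.2.3 (Gastrointestinal toxicity) gives two permissions. For nausea and vomiting: "Nausea, vomiting, or both may be controlled with anti-emetic therapy". For diarrhea: "The use of somatostatin or a somatostatin analogue is allowed to control diarrhea". Neither has a condition or refers to another section. The text goes on to direct diarrhea to standard medications, with electrolyte replacement and laboratory monitoring when appropriate. Grade 3 or 4 diarrhea takes the patient off study.

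Appendix 2 sorts QT-listed drugs into two groups. For Group 1: "Concomitant use of these drugs is not allowed during the study or within 2 weeks of randomization". Group 2 drugs are defined as ones that "at this time lack substantial evidence of causing Torsades de Pointes". They are also ruled out on study, but with an exception: "These drugs will be allowed during the study, at the discretion of the Investigator, if considered absolutely necessary". In that case "the patient must be closely monitored, including regular checks of QTc and electrolytes (reference Section 5.6.2 of the protocol". Octreotide is in Group 2, with its use given as "Endocrine/acromegaly, carcinoid diarrhea".

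Section 8.0 says that drugs listed in Appendix 2 are to be avoided on study and that patients will be told not to start them. It does not mention the Group 2 exception. It has concomitant drugs reviewed at entry and at scheduled assessments, without continuous recording.

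Sections 5.0 and 6.0 schedule one EKG after baseline, the day before surgery or that morning.

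**The concern.** Vandetanib prolongs QT; the protocol lists prolonged QT and Torsades de pointes among its major toxicities. The rule for adding a second QT-listed drug should therefore read the same wherever an investigator looks. For octreotide it does not. Someone managing diarrhea would turn to Section 11.2.3, the section written for that purpose, and could follow it to the letter with no necessity test and no QTc check.

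The same section names low potassium and low magnesium as risk factors for drug-induced arrhythmia, and diarrhea is a setting in which electrolytes can be lost. If QTc did lengthen after such a drug was added, the first scheduled EKG to show it would be the one at the end of dosing. Section 10.1 itself says that the assessment made then comes too late to stop study drug early. Dosing normally lasts 7 to 14 days, and up to 28 if surgery is moved.

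An investigator who does reach Appendix 2 finds an instruction to check regularly and a reference that leads nowhere.

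**Working it through.** The plan states no figure on this point, so the check is to set the texts side by side.

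**Step 1. The rule for octreotide during dosing.**

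| Text | Status | Necessity test | QTc check |
|---|---|---|---|
| 11.2.3, Gastrointestinal toxicity | Allowed, through its class | None | None tied to the drug |
| 8.0 | Avoid | No exception given | None |
| Appendix 2, Group 2 | Not allowed, with an exception | Absolutely necessary, Investigator's discretion | Yes, with electrolytes; no interval |

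The three rows differ. That octreotide is a somatostatin analogue is ordinary pharmacology; the protocol does not say so, although Appendix 2 links the drug to diarrhea.

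**Step 2. The cited monitoring section.** Section 5.0 is one schedule table with footnotes and no numbered subsections. Section 6.0 follows directly. There is no Section 5.6.2. The Group 2 checks therefore have content (QTc and electrolytes) but no frequency.

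**Step 3. Whether another rule supplies the interval.**
- Section 5.0 marks an EKG at baseline and at the post-treatment safety visit: 2 in all, 1 after baseline. The Day 7-14 column has a toxicity evaluation but no EKG or laboratory tests.
- Section 11.2.3 asks for ECGs at least weekly, with electrolytes, once a QTc above 500 ms has been seen and drug withheld. More generally it asks for extra ECGs when prolongation occurs. Both start from prolongation already found. Neither covers the start of a second QT-listed drug.

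**Step 4. The other permissions in Section 11.2.3.** These name no drug, so none contradicts an Appendix 2 entry directly. They lack the same pointer, and Appendix 2 lists drugs of each kind:
- Anti-emetics: ondansetron ("Anti-emetic/nausea and vomiting"), granisetron and dolasetron are in Group 2. Chlorpromazine, droperidol and domperidone are in Group 1, domperidone being marked as unavailable in the U.S.
- Systemic antibiotics for rash: Group 1 includes azithromycin and clarithromycin; Group 2 includes levofloxacin.
- Increased anti-hypertensive medication: Group 2 includes isradipine and nicardipine.

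**Step 5. Whether the texts can be reconciled.** They can in part. A reader who treats Section 8.0 and Appendix 2 as governing the whole study would choose an unlisted agent or use the Group 2 exception. Two gaps remain for that reader: Section 8.0 does not acknowledge the exception, and the checks have no interval.

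**The case against.** The best reply is that the restriction already exists where it belongs. Section 8.0 is the concomitant-drug section and points to Appendix 2. Section 11.2.3 only permits; it tells nobody to use a listed drug. On that view the protocol lacks a cross-reference and no more.

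The risk is also limited. Group 2 drugs are by definition those without substantial evidence of causing Torsades. Entry excludes QTc above 480 ms, potassium outside 4.0-5.0 mmol/L, and calcium or magnesium outside the normal range. Diarrhea goes first to standard medications, and since grade 3 or 4 diarrhea removes the patient, an analogue given during dosing would be for milder diarrhea.

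Most of this stands and sets the weight of the point. It does not remove it. Section 11.2.3 is the more specific text and names the class, so an investigator could reasonably take it as the exception to Section 8.0. The missing interval and the mismatch between Section 8.0 and Appendix 2 remain however carefully the protocol is read.

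A reader might infer more than this. Three such inferences fail:
- *That Section 11.2.3 conflicts with every listed anti-emetic, or permits Group 1 drugs.* It names no anti-emetic, and Appendix 2 bars Group 1 outright.
- *That the Group 2 monitoring is undefined.* Its content is stated; only the interval is absent.
- *That a Group 2 prescription would go unnoticed.* The investigator who gives the drug knows of it. What could be found late is its effect on QTc.

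**Conclusion.** The point holds as an inconsistency in the safety text. Three sections give three rules for octreotide, the monitoring that should accompany it has no interval, and the other supportive-care permissions in Section 11.2.3 have no pointer to Appendix 2. It should be corrected.

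Its size is modest. One listed drug belongs to a class that Section 11.2.3 permits by name. The number of stated intervals for Group 2 checks is 0, and the number of scheduled EKGs after baseline is 1. Endpoint, sample size and analysis are unaffected.

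A reader might be tempted to size the risk from the listing of diarrhea and nausea/vomiting at more than 10% of patients. Those figures suggest that the toxicity text will be consulted. They do not say how many patients would receive a listed drug, or how many would have QTc prolongation as a result. The documents give neither number, and none is claimed here.

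The conclusion rests on octreotide being a somatostatin analogue and on the section numbering as it stands in the protocol.

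**What to change.** Three edits, applying to both arms because treatment is blinded.

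1. At the head of the toxicity-management text in Section 11.2.3, add: *All supportive drugs named below, including somatostatin analogues and anti-emetics, are subject to Section 8.0 and Appendix 2: no Group 1 drug; a Group 2 drug only if the Investigator judges it absolutely necessary, with the Appendix 2 checks.* Placed there, it also covers antibiotics and anti-hypertensives.
2. In Appendix 2, part B, replace the reference to Section 5.6.2 with: *ECG and Ca, Mg and K before the first dose of the Group 2 drug and at least once per week while both drugs continue; the Investigator may shorten the interval.* The week is borrowed from the QTc follow-up in Section 11.2.3, which applies after drug is withheld, so it should be read as a minimum.
3. In Section 8.0, attach the exception to the general rule on avoiding listed drugs: *except a Group 2 drug that the Investigator judges absolutely necessary under Appendix 2.* Leave the patient instruction as it is; the judgment is the Investigator's.

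The cost is a few extra ECGs, electrolyte panels and possibly unscheduled visits, only for patients given a Group 2 drug. Suppose the drug starts on day 2 (an assumption; the documents give no start day) and checks are weekly. The extra checks per patient before the end-of-dosing EKG are then:
- 7-dose course: day 2, so 1.
- 14-dose course: days 2 and 9, so 2.
- 28-day limit: days 2, 9, 16 and 23, so 4.

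The number of such patients is not in the documents. Other patients' schedules do not change.
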